Immunogenicity Evaluations:	
Immunogenicity will be evaluated by the immune response induced in a subset of 400 subjects (300 from the VLP vaccine group and 100 from the placebo group) as measured by the serum HI, MN, and SRH antibody titers on Day 0 and Day 21.
 
A blood sample for exploratory CMI analyses will be collected on Days 0 and 21 for a subset of 400 subjects (the same subset as for HI, MN, and SRH analysis).
 
The North American sites selected for immunogenicity sample collection for this subset of 400 subjects will be pre-defined prior to study start and will target providing a representative age distribution. The subjects identified for the immunogenicity analyses will be also be stratified by age group (1:1 ratio).

Primary Endpoint:	
Efficacy:
 

Occurrences of protocol-defined respiratory illness due to laboratory-confirmed influenza (<math>\geq 14</math> days post-vaccination) caused by influenza viral types/subtypes that are matched (and/or antigenically similar) to the strains covered in the vaccine formulation.

Secondary Endpoints:	
Efficacy:
 

Occurrences of protocol-defined respiratory illness due to laboratory-confirmed influenza (<math>\geq 14</math> days post-vaccination) caused by any influenza viral types/subtypes (matched, mismatched, and un-typed);

Occurrences of laboratory-confirmed influenza (according to protocol defined ILI) illnesses (<math>\geq 14</math> days post-vaccination) caused by influenza viral types/subtypes that are matched (and/or antigenically similar) to the strains covered in the vaccine formulation;

Occurrences of laboratory-confirmed influenza (according to protocol defined ILI) illnesses (<math>\geq 14</math> days post-vaccination) caused by any influenza viral types/subtypes (matched, mismatched, and un-typed);

Occurrences of protocol-defined ILI <math>\geq 14</math> days post-vaccination (confirmed or not).

 
Safety:
 

Percentage, intensity, and relationship to vaccination of immediate complaints (15 minutes post-vaccination);

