Collection of disease burden and health care information 	For each case of respiratory illness (as defined in the protocol), a questionnaire on disease burden (Section 19.2) will be completed by telephone at the end of the 30-day follow up period for the illness, regardless of whether or not a swab is obtained. Subjects will be provided with a memory aid (Section 19.3) to facilitate accurate reporting.				
AEs, SAEs, and NOCDs 	At any time during the study period				
Termination record					

 The end of the surveillance period is targeted as approximately 30 April 2018; however, the duration of surveillance period may be adjusted, based on the observed epidemiology during the season in participating countries.

 Information on past influenza vaccinations for 24 months prior to study entry

 Only a subset of 400 subjects will have a blood draw for CMI and humoral immunogenicity testing. This subset will be comprised of the first subjects enrolled in pre-defined sites in North America; a representative age distribution will be targeted.

 After vaccination, subjects will be instructed on the memory aid and electronic data capture system (eDiary) provided for their use for recording reactions, adverse events, concomitant medication use, and respiratory illness symptoms. They will be reminded of the reportable respiratory illness symptoms that will trigger the need for NP swabbing, as well as of the overall active and passive surveillance process.

 Swabs are to be collected from any subject with a respiratory illness from Day 14 to the end of the surveillance period of the study. If the respiratory illness starts prior to Day 14, swabs are not to be collected, even if symptoms persist beyond Day 14.

 A questionnaire for the collection of disease burden is available in Section 19.2 and includes occurrences of any of the following in association with any respiratory illness with onset from Day 14 to the end of the surveillance period: pneumonia (clinical diagnosis), new onset or exacerbations of pre-existing cardio-respiratory conditions, hospitalizations, emergency room visits, and non-routine medical office visits, as well as any additional diagnoses associated with the illness.

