### **6 TREATMENT ALLOCATION AND BLINDING**

#### **6.1 Randomization**

Randomization will be stratified by site and age group (18 to 49 years of age and 50 to 64 years of age in a 1:1 ratio). Subjects will be randomized to one of two treatment groups, based on a computer-generated randomization schedule prepared by or under the supervision of Medicago before the study.

Potential study subjects will be screened and assigned a subject number. Once all screening procedures, including Day 0 pre-randomization procedures, have been completed and the study eligibility is confirmed by the Investigator, the randomization numbers will be allocated to subjects within the appropriate treatment group by the randomization system.

Once a randomization number has been assigned, it will not be re-used for any reason. No subjects will be randomized into the study more than once. If a randomization number is allocated incorrectly, no attempt will be made to remedy the error once the study vaccine has

---

been dispensed: the subject will continue on the study with the assigned randomization number and associated treatment. The study staff will notify the Sponsor Contact as soon as the error is discovered without disclosing the study vaccine administered. Admission of subsequent eligible subjects will continue using the next unallocated number in the sequence.

The randomization number and treatment will be recorded along with the six-digit subject number for each subject in the investigational product accountability log. The Investigator will not be provided with randomization codes, but it will be possible to unblind the treatment in an emergency situation.

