3. The size of the currently planned placebo-controlled trial (approximately 10,000 subjects) is based on an ARU of  $\geq 2\%$  and it is understood that if the ARU falls below 1.5 %, a second season may be required in order to have sufficient power for hypothesis testing. The use of an active comparator as a control would impact the attack rate estimate that was used in the sample size calculation in two ways, both of which could render the trial non-viable in terms of cost and/or duration:
  - A lower attack rate estimate would be required for an active comparator-controlled study design, resulting in an unrealistic sample size to have adequate power for hypothesis testing;
  - The attack rate estimate for an active comparator control would be significantly more unpredictable, since the efficacy of the currently available seasonal influenza vaccines can range greatly from one season to another (DiazGranados et al., 2012). This unpredictability can, in turn, independent of an increased sample size, lead to a longer study duration in order to achieve sufficient power for hypothesis testing.

Blood samples will be collected from a subset of subjects for humoral immunogenicity analysis, although not all will be analysed. Since blood sample collection is a minimally invasive procedure and the amount of blood collected will be a relatively small amount (Table 5), the benefits of obtaining this data outweigh the small level of risk associated with the collection of samples that may not require analysis.

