3.2 Randomization and blinding

3.2.1 Randomization

Randomization will be used to minimize bias in the assignment of subjects to treatment groups, to increase the likelihood that known and unknown subject attributes (e.g. demographic and baseline characteristics) are evenly balanced across treatment groups and age strata, and to enhance the validity of statistical comparisons across treatment groups.

Approximately 10,000 subjects are planned for randomization in a 1:1 ratio to receive the Quadrivalent VLP Influenza Vaccine at a dose of 30 µg/strain or the placebo. Randomization will be stratified by site and two age groups (18 to 49 years of age and 50 to 64 years of age in a 1:1 ratio).

Individuals will be randomly assigned to a vaccine group by use of an interactive randomization system.

Potential study subjects will be screened and assigned a subject number. Once all screening procedures, including Day 0 pre-randomization procedures, have been completed and the study eligibility is confirmed by the Investigator, the randomization numbers will be allocated to subjects within the appropriate treatment group by the randomization system.

The randomization number and treatment will be recorded along with the six-digit number for each subject in the investigational product accountability log. The Investigator will not be provided with randomization codes, but it will be possible to unblind the treatment in an emergency situation.

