Collection of NP swabs for laboratory confirmation of influenza ⁵	From Day 14 until the end of the influenza surveillance period ¹ , NP swabs will be collected from subjects who report a new or a worsening respiratory illness (as defined in the protocol). Swabs will be collected within 36 hours (preferably within 24 hours) after reporting of the qualifying respiratory illness				

	symptoms.
Collection of disease burden and health care information ⁶	For each case of respiratory illness (as defined in the protocol), a questionnaire on disease burden will be completed by telephone at the end of the 30-day follow up period for the illness, regardless of whether or not a swab is obtained. Subjects will be provided with a memory aid to facilitate accurate reporting.
AEs, Serious Adverse Events (SAEs), and NOCDs ⁷	At any time during the study period
Termination record	X

¹ The end of the surveillance period is targeted as approximately 30 April 2018; however, the duration of surveillance period may be adjusted, based on the observed epidemiology during the season in participating countries.

² Information on past influenza vaccinations for 24 months prior to study entry

³ Only a subset of 400 subjects will have a blood draw for CMI and humoral immunogenicity testing. This subset will be comprised of the first subjects enrolled in pre-defined sites in North America; a representative age distribution will be targeted.

⁴ After vaccination, subjects will be instructed on the memory aid and eDiary provided for their use for recording reactions, AEs, concomitant medication use, and respiratory illness symptoms. They will be reminded of the reportable respiratory illness symptoms that will trigger the need for NP swabbing, as well as of the overall active and passive surveillance process.

⁵ Swabs are to be collected from any subject with a respiratory illness from Day 14 to the end of the surveillance period of the study. If the respiratory illness starts prior to Day 14, swabs are not to be collected, even if symptoms persist beyond Day 14.

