5 SAMPLE SIZE AND POWER

The sample size of approximately 10,000 subjects (5,000 subjects per treatment group) was selected based on the assumption that the Quadrivalent VLP Influenza Vaccine would have a VE of at least 70% and that the attack rate in unvaccinated subjects (ARU) would be 2% or greater for laboratory-confirmed influenza cases caused by vaccine-matched strains. The sample size was chosen to have 90% power to determine whether the lower bound (LB) of the two-sided 95% CI for the primary endpoint would be greater than 40%, assuming a 10% attrition rate.

If the ARU is lower than 2%, but greater than or equal to 1.5%, this sample size will have an 80% power to determine whether the LB of the two-sided 95% CI for the primary endpoint (VE) would be greater than 40%, assuming a 10% attrition rate.

A protocol amendment will be issued to address changes to the enrollment plan or to the study extension into another season to enrol more subjects in the event of insufficient ARU.

Table 3 shows the sample size simulations result. The simulation was repeated 1000 times in order to calculate the power.

Table 3 Sample Size Simulation Result

Placebo Control AR (ARU)	VE (vs placebo)	LB of 95% CI	Power	Sample Size per Group
2%	70%	40%	90%	4430
1.50%	70%	40%	80%	4490

[Note] Under the assumptions of 70% vaccine efficacy (VE) and 2% influenza attack rate (Placebo), we expect a total of 116 to 130 cases of influenza (89 cases for Placebo and 27 cases for VLP in case of 4430 per group considering 10% dropout rate, 100 cases for Placebo and 30 cases for 5000 per group).

If the influenza attack rate is lower than 2%, but greater than or equal to 1.5%, we expect a minimum of 89 total cases.

Immunogenicity Subset

A sample size of 300 subjects (for the VLP vaccine group) was selected to ensure that the LBs of the 95% CI for the co-primary endpoints (SC and SP rates) for each strain meet CBER's criteria with 80% power (individual power is 97.4%).

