8.7 Analysis of immunogenicity

8.7.1 Immunogenicity Evaluations

Immunogenicity will be evaluated by the humoral immune response (HI, MN, and SRH assays) and the CMI response induced in subjects on Days 0 and 21 in a subset of 400 subjects (300 from the VLP vaccine group and 100 from the placebo group) from selected sites. The North American sites selected for this subset of 400 subjects will be pre-defined prior to study start and will target providing a representative age distribution. The subjects identified for the immunogenicity analyses will also be stratified by age group (1:1 ratio).

For the immunogenicity analysis of the HI assays against the homologous strains, the point estimates and the corresponding two-sided 95% CI will be calculated to determine if the CBER criteria for licensure for influenza vaccine are met. The following analyses for the HI assay (homologous strains) will be performed on the IPP:

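### The 300:100 immunogenicity subset cannot come from the written rule of bleeding the first 400 enrolled under 1:1 randomisation, and no document says how the split is to be drawn

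*SAP*

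**What the plan says.** **The split.** SAP 8.7.1 evaluates immunogenicity "in a subset of 400 subjects (300 from the VLP vaccine group and 100 from the placebo group"). The same 300:100 figures stand in the Protocol Synopsis (Immunogenicity Evaluations and Secondary Endpoints), Protocol 10.4.1 and SAP 4.3.1.

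**The power.** SAP 5 (Immunogenicity Subset): "A sample size of 300 subjects (for the VLP vaccine group) was selected to ensure that the LBs of the 95% CI" for seroconversion (SC) and seroprotection (SP) meet the CBER criteria for each strain, with 80% power overall and 97.4% per test. The 100 placebo subjects have no power statement.

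**Who is bled.** Protocol Table 1, footnote 3: "Only a subset of 400 subjects will have a blood draw for CMI and humoral immunogenicity testing". The same footnote in SAP Table 1 adds: "This subset will be comprised of the first subjects enrolled in pre-defined sites in North America", with a representative age distribution as the target. The Synopsis names one stratifier for the subset: "The subjects identified for the immunogenicity analyses will be also be stratified by age group (1:1 ratio").

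**Randomisation.** SAP 3.2.1: "Approximately 10,000 subjects are planned for randomization in a 1:1 ratio to receive the Quadrivalent VLP Influenza Vaccine" or placebo. Protocol 6.1: "Randomization will be stratified by site and age group". No separate 3:1 list or subset stratum is mentioned.

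**Analysed or not.** Protocol 16.1: "Blood samples will be collected from a subset of subjects for humoral immunogenicity analysis, although not all will be analysed".

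**The concern.** The split is a target by arm, while the bleeding rule does not mention arm. Under 1:1 allocation the two cannot both hold unless something further decides who is bled, or which sera are kept, by arm. Three things depend on that missing step.

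- **The stated power.** It belongs to 300 vaccinees. SAP 8.7.2 and 8.7.2.1 run SC and SP for four strains as a fixed sequence that stops at the first miss, so a smaller vaccine group is felt at every step.
- **The number of people bled.** A reader cannot tell whether it is 400 or about 600.
- **The blind.** Protocol 6.2 keeps site staff blinded, apart from those who prepare and give the injections. If bleeding is decided by arm, having blood drawn, or not, carries information about allocation.

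**Working it through.** **1. Reproduce the SAP's power.** Four strains times two criteria gives eight tests. Treated as independent, 0.974^8 = 0.810, which agrees with the stated 80%.

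**2. Vaccinees under the footnote rule.** Inputs: 400 draws (Table 1, footnote 3) and 1:1 allocation (SAP 3.2.1). Expected number: 400 × 0.5 = 200. Binomial(400, 0.5) gives a 95% range of 180 to 220; stratifying by site and age would narrow it. The chance of 300 or more is about 1e-24.

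**3. Readings set against the text.**

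| Reading | 300:100 | Only 400 bled | First enrolled | Bleeding independent of arm |
|---|---|---|---|---|
| Footnote taken literally | no (about 200:200) | yes | yes | yes |
| Bleed more, assay 300:100 | yes | no | yes | yes |
| Select by arm before the draw | yes | yes | no, some early enrollees are passed over | no |

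A further reading of Protocol 16.1, that some of the 400 sera go unassayed, leaves fewer than the 400 that SAP 4.3.1 and 8.7.1 say are analysed.

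**4. Size of over-collection.** To expect 300 vaccinees, 300 / 0.5 = 600 must be bled. The chance of reaching 300 is then 52%; with 645 bled it is 96%.

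**5. What selection by arm would reveal.** A bled subject would be on vaccine with probability 300/400 = 75%, against 50% for a randomised subject. If each arm's quota were filled first-come, the placebo quota would close after about 100 / 0.5 = 200 subjects (95% range 174 to 229) and the vaccine quota after about 600 (553 to 649). Between those points every bled subject would be on vaccine and every unbled one on placebo. No document describes or excludes this.

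**6. Contingency: power if only about 200 vaccinees are bled.** The SAP gives no assumed SC or SP rates, so they are back-solved. Method: two-sided 95% Clopper-Pearson limits (SAP 8.7.2.2.2); pass if the lower limit is at least 40% (SC) or 70% (SP).

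- Fewest responders needed (SC/SP): 138/226 at n = 300; 95/153 at n = 200.
- Rates giving 97.4% per test at n = 300: SC 51.4%, SP 79.8%.
- At those rates and n = 200, power per test is 88.2% (SC) and 89.0% (SP).
- Joint power under independence = (SC power × SP power)^4. At n = 200: (0.882 × 0.890)^4 = 0.38.

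Power to pass all eight tests:

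| True rates above back-solved values | n = 300, independent | n = 200, independent | n = 300, correlation 0.5 | n = 200, correlation 0.5 |
|---|---|---|---|---|
| +0 points | 81% | 38% | 87% | 60% |
| +3 points | 99% | 89% | 99% | 92% |
| +5 points | >99% | 98% | >99% | 98% |

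The correlation is an assumed common latent-normal value. Exclusions from the immunogenicity per-protocol set (SAP 6.4) would lower these figures, and no allowance for them is stated. With an assumed 10% loss and independent tests, joint power at +0/+3/+5 points is 68/98/>99% from 300 bled (n = 270) and 25/81/96% from 200 (n = 180).

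**The case against.** The strongest reply is that the footnote was never the full algorithm. It belongs to a schedule table and omits the 1:1 age stratification given elsewhere. The sections that define the subset do name the arms, five times across the two documents, always as 300:100. Protocol 10.1.2.1 lists treatment assignment by the randomisation system before the baseline blood draw, so selection by arm is feasible in the documented visit order, and the detail may sit in a system specification or study manual outside these documents. Protocol 16.1 may also point to collecting more sera than are assayed. If 300:100 is achieved by any route, nothing in step 6 applies.

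Much of this stands. The intended design is 300:100. A reader might infer from the footnote that the trial will have only 200 vaccinees in the subset and so about 38% power. The documents do not support that: none states a 200:200 split, and the 38% also needs rates stated nowhere and independence of eight tests on the same people. Earlier results point to higher rates, since Protocol 1.3.2.1 reports that the 30 µg dose met the CBER criteria for all four strains, although strains change by season. Nor do the documents show that the blind will be broken; they only leave the safeguard unwritten.

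What does not stand is that the passages agree when read together. As step 3 shows, each route gives up something stated or leaves bleeding dependent on arm, and a quota says what is wanted without saying how it is obtained. A manual cannot settle how many are bled when the protocol gives a limit in one place and implies a different practice in another.

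**Conclusion.** The inconsistency is real and should be fixed. It needs no power calculation: 400 draws from the first enrolled under 1:1 give 180 to 220 vaccinees, against the 300 on which the SAP's 80% rests. What is missing is the step from 1:1 enrolment to 300:100, together with the number bled and the number assayed.

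Any loss of power is conditional on the footnote rule actually being followed. It then ranges from large (81% to 38%, at the lowest rates consistent with 97.4% per test and with independent tests) to negligible (above 99% to 98%, at rates 5 points higher). Positive correlation between tests narrows the gap. The immunogenicity endpoints are secondary; the primary efficacy endpoint and the sample size of about 10,000 are unaffected.

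**What to change.** Keep 300:100 as the design and reconcile footnote 3 of Table 1 (both documents), Protocol 16.1, SAP 5 and SAP 8.7.1. State:

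- how the split is drawn: for example, selection by arm through the randomisation system at the registration step in Protocol 10.1.2.1, or random selection of placebo sera within age stratum by an unblinded party;
- the number bled and the number assayed;
- the safeguards that stop the fact of being bled from revealing allocation to blinded staff and subjects;
- the SC and SP rates behind the 97.4%, and the allowance for exclusions from the immunogenicity per-protocol set.

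Selection through the system costs a short procedure and the blinding safeguards. Selecting sera afterwards keeps bleeding independent of arm, but needs about 600 to 645 subjects bled and a change to the 400 limit. Only if the footnote rule is kept as it stands should the subset be restated as about 200:200 with its power recomputed; that costs wording and a less favourable stated power. None of these changes the efficacy trial.

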6 ANALYSIS POPULATIONS

6.1 Safety Analysis Set (SAS)

The SAS is defined as all subjects who received either the Quadrivalent VLP Influenza Vaccine or the placebo. All safety analysis will be performed using the SAS, according to the treatment the subjects actually received.

6.2 Full Analysis Set (FAS)

The FAS will consist of the subset of subjects in the SAS who were successfully contacted at least once during the surveillance period. Subjects who received the wrong treatment will be analyzed as randomized.

6.3 Per-Protocol (PP) set

The PP set will consist of the subjects who participated in the study until at least the end of the peak period (approximately the end of February for Europe and North America) or for at least five months or until the end of the surveillance period (other countries); had no major protocol deviations related to subject eligibility, the ability to develop a valid immune response, prohibited medication use, or the efficacy analyses; and who received the vaccine or placebo.

Subjects who received the wrong treatment, but for whom the treatment received can be unequivocally confirmed, will be analyzed as treated, provided they have no other deviations that compromise their data.

The PP set will be the primary analysis population for the efficacy and immunogenicity endpoints. The analysis of efficacy and immunogenicity analysis will be repeated using the FAS as the sensitivity analysis.

Note:

Protocol deviations and the definition of the peak influenza period will be reviewed and documented during a blinded data review prior to database lock and confirmed at the time of database lock. Since peak influenza period in each region can vary from year to year, the exact period for individual regions will be defined at the end of the season, based on reported positive influenza tests (regional surveillance reporting). The handling of missing data and whether the potential impact of any protocol deviations require the exclusion of a subject from analyses will also be considered during the blinded data review

